9. PRE-STUDY AND CONCOMITANT INTERVENTION/MEDICATION

Concomitant medications will be documented during screening and updated during the study. Disallowed medications for this study include: See Section 3.3

Concomitant therapies that are disallowed include: See Section 3.3

10. DEVIATIONS FROM THE PROTOCOL

Investigator will notify study sponsor upon identification of a protocol deviation (PD). Major PDs must be reported to the sponsor within 24 hours after discovery of the PD. The Investigator will report deviations per IRB/IEC requirements. All deviations will be tracked and corrective actions implemented as appropriate.

If it becomes necessary for the Investigator to implement a deviation in order to eliminate an immediate hazard to the trial subject, the Investigator may implement the deviation immediately without notification to the sponsor. Within 24 hours after the implemented deviation, the Investigator must notify and provide the rationale to the Sponsor and, as required, the IEC/IRB.

11. STUDY TERMINATION

The occurrence of one or more Unanticipated Serious Adverse Device Effect (USADE), or any SAE where the relationship to study agent cannot be ruled out, may result in stopping further dispensing of test article. In the event of a USADE or SAE, the Sponsor may unmask the treatment regimen for the subject(s) and will discuss this with the Investigator before any further subjects are enrolled.

The Sponsor will determine when a study will be stopped. The Principal Investigator always has the discretion to initiate stopping the study based on patient safety or if information indicates the study's results are compromised.

JJVC reserves the right to terminate the study at any time for any reason. Additionally, the IEC/IRB reserves the right to terminate the study if an unreasonable risk is determined. The study can be terminated by the Principal Investigator at the individual clinical site due to specific clinical observations, if in their opinion, after a discussion with JJVC, it is determined that it would be unwise to continue at the clinical site.

JJVC (and the IEC/IRB and Data Monitoring Committee [DMC], if applicable) will evaluate all adverse events. If it is determined that an adverse event presents an unreasonable risk, the investigation, or that part of the investigation presenting the risk, will be terminated, as soon as possible.

Should the study be terminated (either prematurely or as scheduled), the Investigator will notify the IEC/IRB and Regulatory Authority as required by local regulatory requirements.

12. PROCEDURE FOR HANDLING PRODUCT QUALITY COMPLAINTS

A Product Quality Complaint (PQC) refers to any written, electronic, or oral communication that alleges deficiencies related to the identity, quality, durability, reliability, safety, effectiveness or performance of test articles after they have been released for clinical trial use.

Potential complaints may come from a variety of sources including but not limited to subjects, clinical research associates (CRA), clinical operations managers (COM), medical monitors, and site personnel, etc. The following are not considered product quality complaints:

- Subject satisfaction inquiries reported via “Subjective Questionnaires” and PRO
- Clinical test articles that are stored improperly or damaged after receipt at the investigational site
- Lens replacements that occur due to drops/fall-outs
- Damage deemed by clinicians or clinical staff to be caused by handling by the user, and not indicative of a quality deficiency (i.e. tears, rips, etc.), only in situations where there is no deficiency alleged by the subject

Within 24 hours of site personnel becoming aware that a PQC has occurred, the PQC must be recorded in the EDC system, which will trigger an automatic email notification to the appropriate COM/CRA and Clinical QA representative. In cases where the EDC system in use is not configured to send automatic notifications or when an EDC system is not used, the COM/CRA is responsible for notifying Clinical QA upon discovery that a PQC has occurred.

Upon receipt of the EDC notification, the COM/CRA will contact the study site to collect additional information which will include:

- Date the complaint was received/recorded in the EDC System (Date of Sponsor Awareness)
- Who received the complaint
- Study number
- Clinical site information (contact name, site ID, telephone number)
- Lot number(s)
- Unique Subject Identifier(s)

- Indication of who first observed complaint (site personnel or subject)
- OD/OS indication, along with whether the lens was inserted
- Any related AE number if applicable
- Detailed complaint description (scheduled/unscheduled visit, wear time, symptoms, resolution of symptoms, etc.)
- Eye Care Provider objective (slit lamp) findings if applicable
- Confirmation of product availability for return (and tracking information, if available), or rationale if product is not available for return (Refer to [REDACTED] for test article return instructions)

Once a complaint is received, it will be assessed by the COM, CRA, or trained site personnel to determine if it is an Adverse Event/Serious Adverse Event (AE/SAE). If the complaint results in an AE/SAE, the COM/CRA, or trained site personnel will follow Section 13 of this protocol. If the AE/SAE was potentially the result of a product quality related deficiency, these procedures also applies and will be executed in parallel.

In some cases, a PQC form may be generated in EDC by the site in error. In this event, the PQC forms will be marked “Intentionally Left Blank” or “ILB”. Justification for ILB must be documented.

13. ADVERSE EVENTS

13.1. Definitions and Classifications

Adverse Event (AE) – An AE is “any untoward medical occurrence, unintended disease or injury, or untoward clinical signs (including abnormal laboratory findings) in subjects, users or other persons, whether or not related to the investigational medical device.

Note 1 to entry: This definition includes events related to the investigational medical device or the comparator.

Note 2 to entry: This definition includes events related to the procedures involved.

Note 3 to entry: For users or other persons, this definition is restricted to events related to investigational medical devices.”¹

An AE includes any condition (including a pre-existing condition) that:

1. Was not present prior to the study, but appeared or reappeared following initiation of the study
2. Was present prior to the study, but worsened during the study. This would include any condition resulting from concomitant illnesses, reactions to concomitant medications, or progression of disease states
3. Pregnancy must be documented as an adverse event and must be reported to the clinical monitor and to the Sponsor immediately upon learning of the event

Serious Adverse Event (SAE) – An SAE is any untoward medical occurrence that:

- Results in death
- Is life threatening
- Requires in-patient hospitalization or prolongation of existing hospitalization

- Results in persistent or significant disability/incapacity (e.g., a sight threatening event, a significant persistent or permanent change, impairment, damage, or disruption to the subject's body)
- Is a congenital anomaly/birth defect, or
- Requires intervention to prevent permanent damage (the use of the test article resulting in a condition which requires medical or surgical intervention to preclude permanent impairment of the body structure or a body function). Important medical events that may not result in death, be life-threatening, or require hospitalization may be considered an SAE when, based upon appropriate medical judgment, they may jeopardize the patient or subject and may require medical or surgical intervention to prevent one of the outcomes listed in the above definition

Diagnoses and conditions that are considered Ocular Serious Adverse Events include, but not limited to:

- Microbial Keratitis (MK)
- Iritis (including cells in the anterior chamber)
- Permanent decrease in best spectacle corrected visual acuity equivalent to 2 acuity lines or greater
- Central Corneal Opacity
- Central Corneal Neovascularization
- Uveitis
- Endophthalmitis
- Hypopyon
- Hyphemia
- Penetration of Bowman's Membrane
- Persistent Epithelial Defect
- Limbal cell Damage leading to Conjunctivalization

Significant Adverse Events – Those events that are usually symptomatic and warrant discontinuation (temporary or permanent) of the test article (excluding Serious Adverse Events).

Diagnoses and conditions that are considered Ocular Significant Adverse Events include, but not limited to the following:

- Contact Lens Induced Peripheral Ulcer (CLPU)
- Significant Infiltrative Events (SIE)
- Superior Epithelial Arcuate Lesions (SEALs)
- Any Temporary Loss of > 2 Lines of BSCVA
- Other Grade 3 or higher corneal findings, such as abrasions or edema
- Non-contact lens related corneal events - e.g. Epidemic Keratoconjunctivitis (EKC)
- Asymptomatic Corneal Scar
- Any corneal event which necessitates temporary lens discontinuation > 2 weeks

Non-Significant Adverse Events – Those conditions that are usually asymptomatic and usually do not warrant discontinuation (temporary or permanent) of the test article. However, the Investigator may choose to treat as a precautionary measure.

Diagnoses and conditions that are considered Ocular Non-Significant Adverse Events include, but not limited to the following:

- Non-significant Infiltrative Event (NSIE)
- Contact Lens Papillary Conjunctivitis (CLPC)
- Superficial Punctate Keratitis (SPK)
- Conjunctivitis: Bacterial, Viral, Allergic
- Blepharitis
- Meibomianitis
- Contact Dermatitis
- Localized Allergic Reactions
- Any corneal event not explicitly defined as serious or significant adverse event, which necessitates temporary lens discontinuation < 2 weeks

Adverse Device Effect (ADE) – An ADE is an “adverse event related to the use of an investigational medical device.

Note 1 to entry: This definition includes adverse events resulting from insufficient or inadequate instructions for use, deployment, implantation, installation, or operation, or any malfunction of the investigational medical device.

Note 2 to entry: This definition includes any event resulting from use error or from intentional misuse of the investigational medical device.”¹

Unanticipated Adverse Device Effect (UADE) – Any serious adverse effect on health or safety or any life-threatening problem or death caused by, or associated with, the test article, if that effect, problem, or death was not previously identified in nature, severity, or degree of incidence in the investigational plan, Investigator’s Brochure or protocol, or any other unanticipated serious problem associated with the test article that relates to the rights, safety and welfare of subjects.

13.2. Assessing Adverse Events

In conjunction with the medical monitor, the Investigator will evaluate adverse events to ensure the events are categorized correctly. Elements of categorization will include:

- Seriousness/Classifications (see definition in Section 13.1)
- Causality or Relatedness – i.e. the relationship between the test article, study treatment or study procedures and the adverse event (not related; unlikely related; possibly related; related - see definition in Section 13.2.1)
- Adverse Event Severity – Adverse event severity is used to assess the degree of intensity of the adverse event (mild; moderate; severe for all events - see definition in Section 13.2.2)
- Outcome – not recovered or not resolved; recovering or resolving; recovered or resolved with sequelae; recovered or resolved; death related to adverse event; unknown
- Actions Taken – none; temporarily discontinued; permanently discontinued; other

13.2.1. Causality Assessment

Causality Assessment – A determination of the relationship between an adverse event and the test article. The test article relationship for each adverse event should be determined by the investigator using these explanations:

- Not Related- An adverse event that is not related to the use of the test article, study treatment or study procedures
- Unlikely Related – An adverse event for which an alternative explanation is more likely, e.g. concomitant treatment, concomitant disease(s), or the relationship of time suggests that a causal relationship is not likely
- Possibly Related – An adverse event that might be due to the use of the test article, or to the study treatment or study procedures. An alternative explanation, e.g. concomitant treatment, concomitant disease(s), is inconclusive. The relationship in time is reasonable. Therefore, the causal relationship cannot be excluded
- Related – An adverse event that is listed as a possible adverse effect (device) or adverse reaction (drug) and cannot be reasonably explained by an alternative explanation, e.g. concomitant treatment of concomitant disease(s). The relationship in time is very suggestive, e.g. it is confirmed by de-challenge and re-challenge

13.2.2. Severity Assessment

Severity Assessment – A qualitative assessment of the degree of intensity of an adverse event as determined by the Investigator or reported to him/her by the subject. The assessment of severity is made irrespective of test article, study treatment or study procedure relationship or seriousness of the event and should be evaluated according to the following scale:

- Mild – Event is noticeable to the subject, but is easily tolerated and does not interfere with the subject's daily activities
- Moderate – Event is bothersome, possible requiring additional therapy, and may interfere with the subject's daily activities
- Severe – Event is intolerable, necessitates additional therapy or alteration of therapy and interferes with the subject's daily activities

13.3. Documentation and Follow-Up of Adverse Events

The recording and documenting of adverse events (ocular and non-ocular) begins when the subjects are exposed to the test article, study treatment or study procedure. Adverse events reported before the use of test article, start of study treatment, or study procedures will be recorded as medical history. However, if the condition deteriorates at any time during the study it will be recorded and reported as an AE. Untoward medical events reported after the subject's exit from the study will be recorded as adverse events at the discretion of the Investigator.

Upon finding an adverse event, the Principal Investigator will document the condition in the subject record and in the eCRFs. He/she will complete the Adverse Event /eCRF.

Complete descriptions of all adverse events must be available in the subject record. All Adverse Events including local and systemic reactions not meeting the criteria for "serious adverse events" shall be captured on the appropriate case report form or electronic data system. All adverse events occurring while the subject is enrolled in the study must be documented appropriately regardless of relationship.

It is the Investigator's responsibility to maintain documentation of each reported adverse event. All adverse events will be followed in accordance with applicable licensing requirements. Such documentation will include the following:

- Adverse event (diagnosis not symptom)
- Drawings or photographs (where appropriate) that detail the finding (e.g., size, location, and depth, etc.)
- Date the clinical site was notified
- Date and time of onset
- Date and time of resolution
- Adverse event classification, severity, and relationship to test articles, as applicable
- Treatment regimen instituted, including concomitant medications prescribed, in accordance with applicable licensing requirements
- Any referral to another health care provider if needed
- Outcome, ocular damage (if any)
- Likely etiology
- Best corrected visual acuity at the discovery of the event and upon conclusion of the event

In addition, if an infiltrate(s) is present, he/she will complete the Corneal Infiltrate Assessment eCRF. Where necessary, a culture of the corneal lesion will be collected to determine if the infection is microbial in nature. If cultures are collected, the date of culture collection and laboratory utilized will be recorded.

Changes in the severity of an AE shall be documented to allow an assessment of the duration of the event at each level of intensity to be performed. Adverse events characterized as intermittent require documentation of the onset and duration of each episode. Changes in the assessment of relationship to the Test Article shall also be clearly documented.

Subjects who present with an adverse event shall be followed by the Investigator, within licensure, until all signs and symptoms have returned to pre-treatment status, stabilized, or been satisfactorily resolved. If further treatment beyond licensure is required, the patient will be referred to the appropriate health care provider. The Investigator will use his/her clinical judgment as to whether a subject reporting with an adverse event will continue in the study. If a subject is discontinued from the study, it will be the responsibility of the Investigator to record the reason for discontinuation. The Investigator will also document the adverse event appropriately and complete the Adverse Event eCRF. Any subjects with ongoing adverse events related to the test article, study treatment or study procedures, as of the final study visit date, should be followed to resolution of the adverse event or until referral to an appropriate health care provider, as recommended by the Investigator. Non-ocular adverse events that are not related to the test article, study treatment, or study procedures may be recorded as "ongoing" without further follow-up.

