4.3. Enrollment Target and Study Duration

This is a group sequential, adaptive design where the enrollment will be performed in two phases. In the first phase, up to 160 subjects will be initially enrolled and approximately 150 are targeted to complete the study. An interim analysis will be performed when all subjects have completed Phase 1. The interim analysis will be used to estimate if more subjects are needed. If needed, additional subjects will be added to the study, in phase 2, up to a maximum of 260.

The population to be studied will be healthy male and female volunteers (at least 18 and not more than 70 years old) who are habitual wearers of daily disposable (approximately 80% 1 Day ACUVUE MOIST, approximately 20% any other brand of hydrogel daily disposable contact lens) and have a spectacle astigmatism of <0.75 D in both eyes. Up to 165 subjects will be enrolled to ensure approximately 150 subjects successfully complete the study.

There will be a total of 4 visits and the study duration for Phase 1 will be approximately 3 months:

- Visit 1:** (Day 0): Baseline Screening and Initial Randomization/Dispensing Visit Treatment #1
- Visit 2:** (Day 5-9): 1-Week Follow-Up Visit with first pair of study lenses/Dispensing Visit Treatment #2
- Visit 3:** (Approximately 1 Week from Visit 2): Post wash-out baseline and Dispensing Visit for Treatment #2
- Visit 4:** (Day 5-9 from Visit 3): 1-Week Follow-up Visit with second pair of study lenses and study exit

The Investigator is responsible for ensuring that all subjects entering the study conform to subject selection criteria. The number of subjects targeted for randomization and completion are as follows:

Table 1: Target number of subjects by arm and phase

	Phase 1		Phase 2		All
	Test/Control	Control/Test	Test/Control	Control/Test	Total
Randomization	80	80	50	50	260
Completion	75	75	45	45	250
Number of sites					
Subjects/site (Min-Max)					

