3.23	Dispense	The lenses will be dispensed for a 5-9 day wearing period. During this time, they are required to wear the lenses at least 5 days and at least 8 hours per day that they are worn. 
 • Dispense enough lenses to last the subject to their scheduled follow-up visit. Do not dispense extras* • The lenses will be worn as daily wear/daily disposable only • Rewetting drops are permitted if needed • Subjects will be scheduled for their 1-week follow-up visit and bring their habitual correction with them • Subjects should be instructed to wear the study lenses to the follow-up visit * Note: In the event a lens is lost or damaged, the subject will return to the clinical site for replacement. As much as reasonably possible, a damaged lens and packaging should be returned to the clinical site (wet, if possible) and then returned to the Sponsor. If lens damage is present, complete the Product Quality Complaint Form. The lens will be stored in labeled vial with saline, and clearly differentiated from the other worn lenses that will be shipped back to the Sponsor.

VISIT 4

Subjects should attend wearing their study lenses.

Visit 4: Treatment 2 Follow-Up Visit			
Step	Procedure	Details	
4.1.	Adverse Events and Concomitant Medications Review	Review any changes to the subject's medical history or concomitant medications from the previous study visit. Record any changes, and any adverse events.	
4.2.	Wearing Time	Record the average wearing time and comfortable wearing time.	
4.3.	Compliance	Confirm compliance with the prescribed wear schedule.	
4.4.	Follow-Up Questionnaire (CLUE)	The subject will respond to the Follow-Up Questionnaire.	
4.5.	Subject Reported Ocular Symptoms	Subjects will respond to a verbal open-ended symptoms questionnaire.	
4.6.	Visual Acuity	Record the distance Snellen visual acuity with the contact lenses (OD, OS, and OU) to the nearest letter. Subjects must read the smallest line until at least 50% of the letters are read incorrectly.	

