The final evaluation will ordinarily take place immediately following the last scheduled follow-up visit per the study protocol. It may also take place at any point the subject discontinues the study or is terminated from the study.

Final Evaluation			
Step	Procedure	Details	
F.1	Final Exam Form	Indicate if the subject completed the study successfully. If subject discontinued from the study, indicate the reason.	
F.2	Subjective spherocylindrical Refraction	Perform bare-eye subjective spherocylindrical refraction with a phoropter and record the best	

Final Evaluation		
Step	Procedure	Details
		corrected distance visual acuity to the nearest letter (OD, OS, and OU).
F.3	Comments and Signature	Record any additional information on the page provided and sign the form.

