13.4.1. Reporting Adverse Events to Sponsor

Serious/Significant Adverse Events

The Investigator will inform the sponsor of all serious/significant adverse events occurring during the study period as soon as possible by e-mail, fax, or telephone, but no later than 24 hours following discovery of the event. The Investigator is obligated to pursue and obtain information requested by the Sponsor in addition to that information reported on the eCRF. All subjects experiencing a serious/significant adverse event must be followed up and all outcomes must be reported.

When medically necessary, the Investigator may break the randomization code to determine the identity of the treatment that the subject received. The Sponsor and study monitor should be notified prior to unmasking the test articles.

In the event of a serious/significant adverse event, the Investigator must:

- Notify the Sponsor immediately
- Obtain and maintain in the subject's records all pertinent medical information and medical judgment for colleagues who assisted in the treatment and follow-up of the subject
- Provide the Sponsor with a complete case history which includes a statement as to whether the event was or was not related to the use of the test article
- Notify the IEC/IRB as required by the IEC/IRB reporting procedure according to national regulations

Unanticipated (Serious) Adverse Device Effect (UADE)

In the event of an Unanticipated (Serious) Adverse Device Effect (UADE), the Investigator will submit a report of the UADE to the Sponsor and IEC/IRB as soon as possible, but no later than 24 hours after the Investigator first learns of the effect. This report is in addition to the immediate notification mentioned above.

The Sponsor must conduct an evaluation of the UADE and must report the results of the evaluation to FDA, the IEC/IRB and participating Investigators within 10 working days after the Sponsor first receives notification of the effect.

Non-Serious Adverse Events

All non-serious adverse events, including non-serious adverse device effects, will be reported to the sponsor by the Investigator no later than 2 days from discovery.

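### Section 13.3 leaves the recording of events reported after exit to discretion, and exit is the day the second study lens is removed, so that lens has no mandatory recording after wear

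*Combined protocol and SAP*

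**What the plan says.** Section 13.3 contains two recording rules. One is tied to when an event occurs: "All adverse events occurring while the subject is enrolled in the study must be documented appropriately regardless of relationship". The other is tied to when it is reported: untoward events reported after a subject's "exit from the study will be recorded as adverse events at the discretion of the Investigator". The second rule sets no time window and makes no exception for serious, ocular or device-related events.

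Section 4.3 describes Visit 4 as "1-Week Follow-up Visit with second pair of study lenses and study exit". For that visit, Section 7.2 says "Subjects should attend wearing their study lenses". The lenses are removed at step 4.12. Section 7.2 then adds: "The final evaluation will ordinarily take place immediately following the last scheduled follow-up visit per the study protocol". It also allows the final evaluation at whatever point a subject discontinues. No later contact is scheduled.

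Three other parts of Section 13 bear on events after exit:
- Section 13.3 says that related events ongoing "as of the final study visit date, should be followed to resolution of the adverse event or until referral". This covers events that already exist at the final visit.
- Section 13.4.1 says "The Investigator will inform the sponsor of all serious/significant adverse events occurring during the study period as soon as possible". The term study period is not defined.
- Section 13.4 sets a 24-hour limit for serious or significant events that runs from discovery and is not tied to a study period. The adverse event definition in Section 13.1 has no end date.

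**The concern.** Exit is a natural cut-off only if it comes some time after the last exposure. Here it comes on the last day of exposure. A lens-related lesion that becomes apparent a day or more after Visit 4 is necessarily reported after exit. Under Section 13.3 the investigator may then record it or not.

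The first lens is treated differently. Its wearer stays enrolled through the washout, so recording is mandatory, and there is a slit lamp examination at Visit 3 (step 3.7). A subject who discontinues early comes under the same discretionary rule once the final evaluation is done.

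What is at stake is the completeness and consistency of the adverse event summary. Adverse events are a listed endpoint, and Sections 13.1 and Appendix C name the lens harms concerned, such as infiltrates, peripheral ulcers and microbial keratitis. If recording is discretionary, two sites can treat the same event differently and both comply with the protocol.

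**Working it through.** The plan gives no figure to reproduce on this point. The check sets the rules side by side and then counts the exposures affected.

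**1. Mandatory recording after wear, by lens**

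| | First study lens | Second study lens |
|---|---|---|
| Lens removed | Visit 2, step 2.12 | Visit 4, step 4.12 |
| Subject still enrolled afterwards | 5–9 days (Table 4, step 2.16), or 7–9 days (Sections 4.1, 4.2) | 0 days (final evaluation ordinarily follows at once) |
| Later slit lamp examination | Visit 3, step 3.7 | None |
| Rule for a new event | Mandatory | Investigator's discretion |

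**2. Exposures without a mandatory window**

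Each subject wears two lens types, so there are 2N exposures, of which N are in the second period. This assumes that all randomized subjects complete.
- Phase 1, N = 160: 160 of 320, or 50%.
- Maximum, N = 260: 260 of 520, or 50%.
- With 1:1 sequences, N/2 second-period exposures belong to each lens type: 80 Test and 80 Control in Phase 1, 130 and 130 at the maximum.

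**3. Internal consistency of Section 13.3**

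Take a lesion that begins the day before Visit 4 and is reported the day after. It occurred while the subject was enrolled, so recording is mandatory. It was reported after exit, so recording is discretionary. Both sentences apply and they disagree. This does not depend on any assumption about latency.

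**4. Illustrative share of events first showing after exit**

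The documents give no time to onset. Assume that events originate at a constant rate over L days of wear and each shows d days later. Events originating in the last d days of wear then show after exit, so the second-period share is d/L.

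| Delay d | L = 5 | L = 7 | L = 9 |
|---|---|---|---|
| 1 day | 1/5 = 20% | 1/7 = 14% | 1/9 = 11% |
| 2 days | 2/5 = 40% | 2/7 = 29% | 2/9 = 22% |
| 3 days | 3/5 = 60% | 3/7 = 43% | 3/9 = 33% |

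If both periods have the same rate and length, the share of all events is half of this. For d = 2 that is 20% to 11%. First-lens events with these delays still fall inside a washout of at least 5 days.

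**5. Illustrative counts**

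Let p be an assumed risk, per exposure, of an event that shows only after wear ends. Then N × p such events are expected among second-period exposures, and the chance of at least one is 1 − (1 − p)^N. For N = 260:
- p = 0.1%: 0.26 expected, chance 0.23.
- p = 0.5%: 1.3 expected, chance 0.73.
- p = 1%: 2.6 expected, chance 0.93.

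For N = 160 the chances are 0.15, 0.55 and 0.80. The documents support no particular value of p.

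**The case against.** The strongest reply is that other text does not end at exit.
- The 24-hour duty in Section 13.4 runs from discovery, and the definition in Section 13.1 is open-ended. Section 13.3 also says, without a time limit, that subjects presenting with an adverse event are followed.
- The report of an unanticipated adverse device effect runs from when the investigator learns of it. Its definition can reach a known effect whose severity or incidence was not previously identified.
- Section 12 offers a parallel route through product complaints where a deficiency is alleged.
- Visit 4 itself includes adverse event review, symptoms and biomicroscopy after lens removal.

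Much of this stands, and it rules out some stronger readings. A reader might infer that a serious event after exit cannot be notified or cannot reach the study stop. The documents do not support that: the discovery duty has no stated end, and both the synopsis and Section 11 turn on the occurrence of an event, not on a completed form. A reader might also infer a bias in favour of Test. The loss goes by period, the sequences are 1:1, and Section 2.2 has adverse events evaluated descriptively, so no such bias follows. Nor is any share in the illustrative table an upper limit on the loss, because each rests on an assumed delay and length of wear. Appendix C warns that eye problems can develop rapidly, which would favour short delays.

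The other provisions do not remove the gap. The duty in Section 13.4 applies to adverse events, and Section 13.3 leaves it to the investigator whether a report after exit is recorded as one. The complaint route needs an alleged deficiency. The device-effect route covers only unanticipated serious problems. For an ordinary, known lens harm the discretionary sentence is the specific rule on recording.

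**Conclusion.** The point holds as a gap in mandatory recording and an inconsistency within Section 13. Under Section 13.3 the second study lens has 0 days of mandatory recording after wear, against 5–9 days (7–9 in Sections 4.1 and 4.2) for the first. A known harm from the second lens that is reported after exit can be left out of the summary without breach of that section. For events that begin before exit and are reported after it, the section contradicts itself. It is also in tension with Sections 13.1 and 13.4.

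The loss lowers the sensitivity of the safety summary for both lenses about equally. Its size is unknown, and absolute counts are likely to be small. The range of 22% to 40% of second-period events holds only for an assumed 2-day delay, a constant rate and 5 to 9 days of wear. The Visit 4 slit lamp may show early signs of some of these events, which would reduce the share. The change is worth making because it is cheap and improves the capture of safety events.

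**What to change.** In Section 13.3, replace the discretionary sentence with mandatory recording of:
- (a) any event with onset before exit, whenever it is reported; and
- (b) any ocular event, and any event judged possibly related or related, that is reported to the site within a fixed interval after the last study-lens wear. The sponsor should set the interval. The longest washout already in the schedule, 9 days, is one example.

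For each such event, record the onset date and the last study lens worn, and grade causality under Section 13.2.1. There should be no automatic attribution to the study lens: subjects will usually have gone back to habitual lenses, and Section 3.1 expects about 80% of them to wear 1-Day ACUVUE MOIST.

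In Section 13.4.1, define the study period to match. Reconcile Sections 13.1, 13.3, 13.4 and 13.4.1 with each other and with the stop text. The synopsis says that a qualifying event will stop further dispensing, whereas Section 11 says that it may. Which of these is intended is for the sponsor to settle.

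The cost is a few sentences in Section 13, with no added visit or procedure. The downside is that a few events caused by resumed habitual lenses will also be recorded. The onset date and the causality grade allow these to be identified.
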